4.7. Study Treatment Compliance (%)

4.7.1. Study Treatment Compliance in the Run-in Period

Run-in period study treatment compliance (%) = [(Quantity of run-in period investigational product prescribed – Quantity of run-in period investigational product returned)]/(Duration of administration of investigational product in the run-in period) x 100

The values will be displayed rounded off to the first decimal place.

4.7.2. Study Treatment Compliance in the Treatment Period

Treatment period study treatment compliance (%) = [(Quantity of treatment period investigational product prescribed – Quantity of treatment period investigational product returned)]/(Duration of administration of investigational product in the treatment period) x 100

The values will be displayed rounded off to the first decimal place.

4.8. eGFR

eGFR (mL/min/1.73 m²) = 194 x Serum creatinine^{-1.094} x Actual age of the subject in years^{-0.287}
(females: x 0.739)

4.9. eGFR % Decline

eGFR % decline = [(eGFR value at the measurement time point in question – Mean of the eGFR value on the first day of the run-in period and the eGFR value on the first day of the treatment period) / Mean of the eGFR value on the first day of the run-in period and the eGFR value on the first day of the treatment period] x 100

The values will be displayed rounded off to the first decimal place.

4.10. Periods of Assessment of Efficacy Endpoint Events

4.10.1. Time to Initial Event Onset (in days)

Time to initial event onset = Day of initial event onset – First day of the treatment period + 1

4.10.2. Time to Censoring (in days)

1. Subjects for whom the date of the visit at Week 4 of the follow-up observation period can be obtained

Time to censoring = Date of the visit at Week 4 of the follow-up observation period – First day of the treatment period + 1

2. Subjects for whom the date of the visit at Week 4 of the follow-up observation period can not be obtained

Time to censoring = Final assessment time point^{*1} – First day of the treatment period + 1

^{*1}Final assessment time point

If the day of discontinuation can be obtained: Day of discontinuation

If the day of discontinuation cannot be obtained: Day of the final scheduled visit^{*2}

^{*2}Day of the final scheduled visit

The latest date will be used, regardless of the allowable time window

4.11. Urine ACR (First Morning Void Urine)

- Urine ACR (First Morning Void Urine)

The median of 3 measured values will be used. If only 2 measured values are available, then the median of these 2 measured values will be used, and if only 1 measured value is available, this value will be used. These values will be displayed rounded off to the first decimal place. Additionally, the last date of the dates on which the 3 (or 2) measurements were performed will be considered the date of measurement.

- Log-transformed urine ACR

The natural log will be used for log transformation.

- Geometric mean urine ACR

Geometric mean urine ACR = Value obtained by the inverse transformation of the arithmetic mean of the log-transformed urine ACR values

- Change in the log-transformed value

Change in the log-transformed urine ACR = Value obtained by the log transformation of the urine ACR at each measurement time point – Value obtained by the log transformation of the urine ACR on the first day of the treatment period

4.12. Adverse Drug Reaction

Adverse events for which it has been determined that there is a “reasonable possibility” of there being a causal relationship to the investigational product will be handled as adverse reactions.

4.13. Period of Assessment of the Incidence Per 1000 Person-Years of Each Safety Endpoint

1. Subjects for whom the date of the visit at Week 4 of the follow-up observation period can be obtained

Period of assessment of the incidence per 1000 person-years (in years) = (Day of the visit at Week 4 of the follow-up observation period – First day of the treatment period + 1)/365.25

2. Subjects for whom the date of the visit at Week 4 of the follow-up observation period can not be obtained

Period of assessment of the incidence per 1000 person-years (in years) = (Final assessment time point^{*1} – First day of the treatment period + 1)/365.25

^{*1}Final assessment time point

If the day of discontinuation can be obtained: Day of discontinuation

If the day of discontinuation cannot be obtained: Day of the final scheduled visit^{*2}

^{*2}Day of the final scheduled visit

The latest date will be used, regardless of the allowable time window

5. Analysis Sets

The analysis of efficacy is performed in the full analysis set (FAS). In addition, a secondary analysis of the primary endpoint will be performed in the per-protocol set (PPS), as well. Safety analysis is performed in the safety analysis set. The data sets analyzed are defined below. The study sponsor finalizes the details of how the subjects are handled by the time of the database lock.

5.1. Efficacy Analysis Sets

(1) Efficacy Analysis Sets

1) FAS

The analysis sets consisting of all randomized subjects other than the following constitute the FAS.

- Subjects who were not type 2 diabetes mellitus patients with Stage 3 diabetic nephropathy (overt nephropathy)
- All subjects who did not take the investigational product at all
- All subjects for which no post-randomization efficacy data are available

2) PPS

The PPS is the FAS, minus the following subjects.

- Subjects who have deviated from the inclusion criteria
- Subjects who have met the exclusion criteria
- Subjects who have violated the stipulations about the prohibited concomitant drugs
- Subjects with a rate of compliance with the investigational product of 75% or lower
- Subjects with treatment periods shorter than 52 weeks

5.2. Safety Analysis Sets

The analysis sets consisting of all randomized subjects other than the following constitute the safety analysis sets.

- All subjects who did not take the investigational product at all
- All subjects for which no post-randomization safety data are available

6. Handling of Data

The data handling procedures are described below, except for issues that are determined by the study sponsor's case review board.

6.1. Handling of Missing Values

When test values are missing or reported as reference data, or can not be measured because of, for example, a problem with the test sample, this parameter will be handled as missing. If the data (e.g., test

values) required for derivation include even 1 missing or uncollected value, the derived variable will be considered missing.

6.2. Handling of Time Point Data When Tabulating the Data by Evaluation Time Point

Table 6.2: Test/Observation Schedule Allowable Time Windows

Assessment Time Point		Reference Date	Allowable Window
Screening period	First day of the screening period	—	*1
Run-in period	First day of the run-in period	-14 days	-17 days to -11 days
Treatment period	First day of the treatment period* ² (Week 2 of the run-in period)	0 days	—
	Week 4 of the treatment period	28 days	14 days to 42 days
	Week 8 of the treatment period	56 days	43 days to 70 days
	Week 12 of the treatment period	84 days	71 days to 98 days
	Week 16 of the treatment period	112 days	99 days to 126 days
	Week 20 of the treatment period	140 days	127 days to 154 days
	Week 24 of the treatment period	168 days	155 days to 182 days
	Week 28 of the treatment period	196 days	183 days to 210 days
	Week 32 of the treatment period	224 days	211 days to 238 days
	Week 36 of the treatment period	252 days	239 days to 266 days
	Week 40 of the treatment period	280 days	267 days to 294 days
	Week 44 of the treatment period	308 days	295 days to 322 days
	Week 48 of the treatment period	336 days	323 days to 350 days
	Week 52 of the treatment period	364 days	351 days to 378 days
	Week 56 of the treatment period	392 days	379 days to 406 days
	Week 60 of the treatment period	420 days	407 days to 434 days
	Week 64 of the treatment period	448 days	435 days to 462 days
	Week 68 of the treatment period	476 days	463 days to 490 days
	Week 72 of the treatment period	504 days	491 days to 518 days
	Week 76 of the treatment period	532 days	519 days to 546 days
	Week 80 of the treatment period	560 days	547 days to 574 days
	Week 84 of the treatment period	588 days	575 days to 602 days
	Week 88 of the treatment period	616 days	603 days to 630 days
	Week 92 of the treatment period	644 days	631 days to 658 days
	Week 96 of the treatment period	672 days	659 days to 686 days
	Week 100 of the treatment period	700 days	687 days to 714 days
	Week 104 of the treatment period	728 days	715 days to 742 days
Treatment period discontinuation		The day of treatment period discontinuation	Within 7 days of the day of treatment period discontinuation
Week 4 of the follow-up observation period		Week 104 of the treatment period (or the day of treatment period discontinuation)	28 to 42 days after the last day of the treatment period

*1: The first day of the run-in period should be within 4 weeks of the first day of the screening period.

*2: The first day of the treatment period is the day of the initial prescription of the treatment period investigational product.

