6.2.1. Tabulation by eGFR Assessment Time Point

When tabulating the eGFR at each assessment time point, data that fall within the allowable time windows defined in “Table 6.2: Test/Observation Schedule Allowable Time Windows” will be used. For data that have been reported as having been collected at treatment period discontinuation, data that were collected within the allowable time window for the day of treatment period discontinuation will be used. Although a data tabulation at discontinuation will not be performed, data that have been collected within the allowable time window for the day of treatment period discontinuation that are also within the allowable time window for the time point in question will as a rule be used as data for that time point. In addition, if multiple measurements have been taken within an allowable time window, data from the test that was performed on the day closest to the target day will be used. If there are multiple measurements, and the difference in the numbers of days between the day of each measurement and the target day are the same, then the data that were collected earlier will be used.

6.2.2. Tabulation of the eGFR at Each Assessment Time Point When Imputing Data Outside the Allowable Time Window

When tabulating the eGFR data for each assessment time point, the data stipulated in 6.2.1 will be combined with data imputed by means of multiple imputation (██████████) for data for which the assessment time point was outside the allowable time window. A linear regression model with the data at each assessment time point from the first day of the treatment period until Week 88 of the treatment period as the explanatory variable will be used to replace missing values for each assessment time point from Week 4 of the treatment period through Week 104 of the treatment period. It will be assumed that the pattern of missing values is non-monotonic.

6.2.3. Tabulation of Endpoints Other Than the eGFR and Urine ACR at Each Assessment Time Point

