6.2.4. Tabulation of the Urine ACR Endpoints at Each Assessment Time Point

When tabulating the urine ACR endpoints at each assessment time point, if the date of the visit falls within the allowable time window defined in “Table 6.2: Test/Observation Schedule Allowable Time Windows,” then data that have been collected within a 1-week period that includes the visit day will be used as data for that time point. Also, if the day of the visit at discontinuation falls within the allowable time window of the day of discontinuation in the treatment period and the allowable time window for the time point data, then data that were obtained within a 1-week period that includes the day of the visit at discontinuation will be used as the data for that time point. Data will not be replaced with data from outside the allowable time windows. In addition, if multiple measurements were taken within the allowable time window, then the visit day that was closest to the target date will be used. If the difference (in the number of days) between the day of the measurement and the target day is the same for each of two measurements, then the earlier day will be used.

6.3. Handling of eGFR Data at the End of the Treatment Period (Analysis of 7.6.1.3)

When tabulating eGFR data at the end of the treatment period, the data collected at Week 104 of the treatment period, as defined in “Table 6.2: Test/Observation Schedule Allowable Time Windows” will be used. However, if any data from Week 104 of the treatment period are missing, then these data will be imputed as indicating that an eGFR decline has occurred.

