7.6.1.2. Secondary Analysis

Analysis population(s): FAS, PPS

Analysis parameter(s): Proportion of subjects with a decline of 30% in the eGFR at Week 104 of the treatment period

Analysis method:

In accordance with “6.2.2. Tabulation of the eGFR at Each Assessment Time Point When Imputing Data Outside the Allowable Time Window,” a dataset will be prepared using [REDACTED]. The estimated values from this dataset, and the variance thereof, will be combined using Rubin’s rule, and the proportion of subjects with a decline of 30% in the eGFR at Week 104 of the treatment period, and the 95% confidence interval thereof, will be shown for each treatment group.

In addition, for each of these datasets, a logistic regression model will be applied with a decline of 30% in the eGFR at Week 104 of the treatment period as the target variable, treatment group and the stratification factor eGFR on the first day of the run-in period (≥ 30 and < 45 , ≥ 45 and < 60 , ≥ 60 and < 90) as factors, and the urine ACR (first morning void urine) as covariates, and the estimates and variances thereof will be calculated and combined in accordance with Rubin’s rule. An intergroup comparison of these results will be performed, and the odds ratio of a 30% decline in the eGFR in the TA-7284 group relative to the placebo group at Week 104 of the treatment period, and the 95% confidence interval thereof, will be presented.

Listings

Analysis population(s): Randomized subjects

7.6.1.3. Other Analysis 1

Analysis population(s): FAS, PPS

Analysis parameter(s): Proportion of subjects with a decline of 30% in the eGFR at Week 104 of the treatment period

Analysis method:

The proportion of subjects with a 30% decline in the eGFR at Week 104 of the treatment period, and the 95% confidence interval thereof, will be presented for each treatment group for the dataset obtained through the replacement of missing values at Week 104 of the treatment period in accordance with “6.3 Handling of eGFR Data at the End of the Treatment Period.” The point estimate for the difference between the groups (placebo group minus TA-7284 group) and the 95% confidence interval according to the Farrington-Manning method will also be shown.

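### A lost treatment Day 1 eGFR leaves the two-value baseline missing, and with it the subject's 30% and 40% responder status in the primary analysis, although a run-in eGFR is available

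*SAP*

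**What the plan says.** **Baseline.** SAP 4.5.2 (change, percent change) and 4.9 (percent decline) both compare with the average of two eGFR values, run-in Day 1 and treatment Day 1. Neither section says what to do if only one of the two exists. Both stand in SAP section 4, which defines the derived variables.

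**Missing inputs.** SAP 6.1 treats a result that could not be measured, for instance because of a sample problem, as missing. It adds that if the data "required for derivation include even 1 missing or uncollected value, the derived variable will be considered missing".

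**Imputation.** In SAP 6.2.2 a linear regression model "will be used to replace missing values for each assessment time point from Week 4 of the treatment period through Week 104". It takes "data at each assessment time point from the first day of the treatment period until Week 88 of the treatment period as the explanatory variable". Treatment Day 1 is therefore a predictor and not a stated target; run-in Day 1 is neither.

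**Missing counted as decline.** SAP 6.3 gives the rule for Other Analysis 1 (7.6.1.3): "if any data from Week 104 of the treatment period are missing, then these data will be imputed as indicating that an eGFR decline". The subject is thus classed as having declined. SAP 7.6.1.3 then analyses the "dataset obtained through the replacement of missing values at Week 104 of the treatment period in accordance with" that section.

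**Fallbacks elsewhere.** Blood pressure (SAP 4.4) and urine ACR (SAP 4.11) may rest on fewer measurements. For ACR: "If only 2 measured values are available, then the median of these 2 measured values will be used".

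**The concern.** The run-in eGFR is secured by design. It decides inclusion criterion (8) in Protocol 3.2 and the randomisation stratum in SAP 2.3. Nothing secures the treatment Day 1 eGFR in the same way: no eligibility criterion depends on it, and under Protocol 8.2.4 the first dose is taken on the day of first prescription. If the central laboratory later finds that sample unusable, no second pre-dose sample can be drawn. The subject is by then randomised and treated. The FAS definition in SAP 5.1 does not remove a subject for a missing baseline value.

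Such a subject may have a valid pre-treatment eGFR and a measured Week 104 eGFR and still contribute nothing to the primary comparison, because a general rule about derived variables discards the one baseline value that exists. The eGFR change and percent change are lost at every visit as well. Where 6.3 is unclear, two programmers working from the same data could also reach different denominators.

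**Working it through.** **1. The plan's own figure.** SAP 2.5 gives 300 subjects, 150 per group. The rationale is not in the public copy, so event rates, power and dropout allowance are unavailable and this figure cannot be reproduced. The question is mainly one of tracing the rules.

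**2. Trace for an FAS subject with a run-in eGFR and no treatment Day 1 eGFR.**

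| Analysis | Week 104 measured | Week 104 missing |
|---|---|---|
| 7.6.1.1 primary, multiple imputation | No baseline (4.9 with 6.1): status missing | Week 104 is an imputation target, but there is no baseline: status missing |
| 7.6.1.2 logistic, multiple imputation | Missing | Missing |
| 7.6.1.3 missing counted as decline | Unclear: the Week 104 eGFR is present but the decline derived from it is missing | Counted as a decline; no baseline needed |
| 7.6.1.4 observed data | Missing | Missing |

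The 40% analyses in 7.6.2.1 follow the same four methods and give the same results.

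**3. What the unclear cell means.** If 6.3 is taken to cover a missing decline as well as a missing Week 104 eGFR, each such subject adds 1/150 = 0.67 percentage points to the decline proportion in an arm of 150, despite a measured Week 104 value. If it is not, the subject is lost there too.

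**4. Mixed model for eGFR (7.6.2.3).** The outcome is change from the two-value mean, so it is missing at every visit. The model covariate is stated as the treatment Day 1 value, repeated in 7.6.3.1, and is missing too. Repairing only 4.5.2 and 4.9 would therefore not bring the subject back into this model.

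**5. Scale, for illustration only.** Let m be the share of subjects without treatment Day 1 eGFR, equal in both arms, so n = 150(1 − m) per arm. Both m and the event rates are assumptions. Two-sided alpha is 0.05 (SAP 7.1.3). With p̄ = (p1 + p2)/2,

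power = Φ( [ |p1 − p2| − 1.96·√(2p̄(1 − p̄)/n) ] / √( [p1(1 − p1) + p2(1 − p2)]/n ) ).

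Example, 30% vs 15%, n = 150: (0.15 − 1.96 × 0.04822)/0.04743 = 1.170, power 87.9%. With m = 2%, n = 147: (0.15 − 1.96 × 0.04871)/0.04792 = 1.138, power 87.25%.

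| Placebo vs active | m = 0 | 2% (n = 147) | 5% (n = 142.5) | 10% (n = 135) | Loss at 2% (points) |
|---|---|---|---|---|---|
| 20% vs 10% | 68.1 | 67.2 | 65.8 | 63.5 | 0.88 |
| 30% vs 15% | 87.9 | 87.3 | 86.2 | 84.3 | 0.65 |
| 35% vs 20% | 83.2 | 82.5 | 81.3 | 79.2 | 0.75 |
| 40% vs 25% | 79.5 | 78.7 | 77.4 | 75.2 | 0.81 |

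At 2%, which is 0.02 × 300 = 6 subjects, the loss is below 1 point in every row. This is a plain two-proportion calculation without imputation. It shows scale and does not reconstruct the plan's power.

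**The case against.** The strongest reply is that this is a rare event with a small effect. Treatment Day 1 is a required visit that defines day 0, few samples will fail, and failure should not depend on treatment. That stands: the consequence is lost precision, and no bias has been shown.

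A second reply is that the plan may deal with the case elsewhere. SAP section 6 excepts issues decided by the sponsor's case review board, and the name of the imputation method is blacked out. A method for non-monotone missingness might fill treatment Day 1 internally. This stands only in part. Board discretion is not a prespecified rule, and the visible text limits the targets to Weeks 4 to 104.

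Third, the blood pressure and ACR fallbacks concern replicates belonging to one visit, whereas the eGFR baseline joins two visits and the protocol defines it as their average. The analogy is indeed loose, and a one-value baseline does vary the protocol definition for the subjects concerned. It would rest on the value used to select them. That is a reason to record the change, not a reason to discard the subjects.

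Three stronger readings are tempting, and the documents do not support them:

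- A reader might infer that the subject falls out of every analysis of the primary endpoint. SAP 7.6.1.3 keeps a subject whose Week 104 value is also missing, as a decline.
- A reader might infer that a run-in visit outside days −17 to −11 also destroys the baseline. The window rule in 6.2.1 is about tabulation by time point; 4.5.2 and 4.9 define baseline by named visit day and do not cite Table 6.2. SAP 7.6.2.3 does describe the two-value baseline when presenting the 6.2.1 data, so the point deserves a sentence, but exclusion is not stated. Treatment Day 1 has no window.
- A reader might infer that the rule contradicts the FAS definition. The subject stays in the FAS; what is missing is the endpoint value.

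**Conclusion.** The gap is real and confined to one realistic case: a treatment Day 1 eGFR that is lost or cannot be measured. As written, that subject has no 30% or 40% responder status in three of the four analyses of each endpoint, including the primary one. In the fourth the subject is either counted as a decline or left undetermined. A lost run-in value is unlikely in a properly randomised subject.

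The documents give no frequency, so the size can only be illustrated: less than 1 percentage point of power if 2% of subjects are affected, and 3.6 to 4.6 points at an extreme 10%, under the assumed rates. The conclusion rests on the visible wording of 6.1 and 6.2.2, with the method name and appendices unavailable. It is worth correcting because the rule discards usable data in the primary analysis and the remedy is cheap.

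**What to change.** Before database lock:

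1. In SAP 4.5.2 and 4.9, state: *If only one of the two eGFR values is available, that value is the baseline; section 6.1 does not apply to this mean.*
2. Clarify that the run-in Day 1 value used for stratification enters the baseline whatever its position relative to the Table 6.2 window.
3. In SAP 6.3, state that a measured Week 104 eGFR is classified against this baseline, and that only a missing Week 104 eGFR is counted as a decline.
4. When treatment Day 1 is missing, use the same baseline as the covariate in the eGFR mixed model (7.6.2.3, with 7.6.3.1 and the subgroup version in 7.6.3.8 made consistent) and as the baseline predictor in 6.2.2.
5. Record the fallback in SAP section 9, since the protocol defines the endpoint against the average of both values.

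The cost is a few sentences and a small programming change. The downside is a slightly noisier baseline for a few subjects.
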